8.2.2 Serious adverse events (SAEs)

A serious adverse event is any untoward medical occurrence or effect that at any dose:

- results in death;
- requirement of hospitalisation or prolongation of existing inpatients' hospitalisation for reasons not related to cellulitis
- is life threatening (at the time of the event);
- results in persistent or significant disability or incapacity;
- is a congenital anomaly or birth defect;
- any other important medical event that may not result in death, be life threatening, or require hospitalization, may be considered a serious adverse experience when, based upon appropriate medical judgement, the event may jeopardize the subject or may require an intervention to prevent one of the outcomes listed above.

The sponsor will report the SAEs through the web portal *ToetsingOnline* to the accredited METC that approved the protocol, within 15 days after the sponsor has first knowledge of the serious adverse reactions. This holds true for both the coordinating center as well as the participating centers (see PIs as stated above).

SAEs that result in death or are life threatening should be reported expedited. The expedited reporting will occur not later than 7 days after the responsible investigator has first knowledge of the adverse reaction. This is for a preliminary report with another 8 days for completion of the report.

Of note, since a significant part of included patients is expected to be readmitted to the hospital due to relapse of cellulitis, the requirement of hospitalisation or prolongation of existing inpatients' hospitalisation due to cellulitis is not considered a SAE and will not be reported to the METC but will be subjected by monitoring by the DSMB. SAE's will be reported until the patient reaches the end of study. To facilitate SAE reporting in the period between day 28 and day 90, participants will receive a card on day 28 with instructions to contact the study team in case any SAE occurs.

8.2.3 Suspected unexpected serious adverse reactions (SUSARs)

Adverse reactions are all untoward and unintended responses to an investigational product related to any dose administered.

Unexpected adverse reactions are SUSARs if the following three conditions are met:

1. the event must be serious (see chapter 8.2.2);
2. there must be a certain degree of probability that the event is a harmful and an undesirable reaction to the medicinal product under investigation, regardless of the administered dose;
3. the adverse reaction must be unexpected, that is to say, the nature and severity of the adverse reaction are not in agreement with the product information as recorded in:
 - Summary of Product Characteristics (SPC) for an authorised medicinal product;
 - Investigator's Brochure for an unauthorised medicinal product.

The sponsor will report expedited the following SUSARs through the web portal *ToetsingOnline* to the METC:

- SUSARs that have arisen in the clinical trial that was assessed by the METC;
- SUSARs that have arisen in other clinical trials of the same sponsor and with the same medicinal product, and that could have consequences for the safety of the subjects involved in the clinical trial that was assessed by the METC.

The remaining SUSARs are recorded in an overview list (line-listing) that will be submitted once every half year to the METC. This line-listing provides an overview of all SUSARs from the study medicine, accompanied by a brief report highlighting the main points of concern.

The expedited reporting of SUSARs through the web portal *ToetsingOnline* is sufficient as notification to the competent authority.

The sponsor will report expedited all SUSARs to the competent authorities in other Member States, according to the requirements of the Member States.

The expedited reporting will occur not later than 15 days after the sponsor has first knowledge of the adverse reactions. For fatal or life threatening cases the term will be maximal 7 days for a preliminary report with another 8 days for completion of the report. This holds true for both the coordinating center as well as the participating centers (see PIs as stated above).

8.3 Annual safety report

In addition to the expedited reporting of SUSARs, the sponsor will submit, once a year throughout the clinical trial, a safety report to the accredited METC, competent authority, and competent authorities of the concerned Member States.

This safety report consists of:

- a list of all suspected (unexpected or expected) serious adverse reactions, along with an aggregated summary table of all reported serious adverse reactions, ordered by organ system, per study;
- a report concerning the safety of the subjects, consisting of a complete safety analysis and an evaluation of the balance between the efficacy and the harmfulness of the medicine under investigation.

8.4 Follow-up of adverse events

All AEs will be followed until they have abated, or until a stable situation has been reached. Depending on the event, follow up may require additional tests or medical procedures as indicated, and/or referral to the general physician or a medical specialist. SAEs need to be reported till end of study within the Netherlands, as defined in the protocol.

8.5 Data Safety Monitoring Board (DSMB)

The assessment of data quality and the monitoring of compliance with the protocol, monitoring of trial conduct and monitoring of evidence for treatment harm will be performed by an independent data monitoring team of the AMC, Amsterdam, the Netherlands.

A Data Safety Monitoring Board (DSMB) will receive and review the progress and accruing data of this trial and will provide advice on the conduct of the trial to the Trial Steering Committee (TSC).

An independent DSMB will evaluate mortality after 198 patients have completed the trial. Given the expected low mortality rates^{10,19}, the power to detect differences in mortality at this stage will be very low. Therefore, the DSMB will qualitatively evaluate all deaths for their possible relation with the given treatment. Only in case of striking differences between the two arms they will inform investigators and the METC.

Members of the DSMB will be:

- Chair: prof. dr. [name], internist-infectiologist, President of the Dutch Association for Infectious Diseases (VIZ), LUMC, Leiden, the Netherlands
- Dr. [name], internist-infectiologist, President of the Dutch Association of AIDS-treating Physicians (NVHB), AMC, Amsterdam, the Netherlands
- Dr. [name], methodologist, Clinical Research Unit, AMC, Amsterdam, the Netherlands

A separate Charter will describe the roles and responsibilities of the independent DMC, including the timing of meetings, methods of providing information to and from the DMC, frequency and format of meetings and relationships with other committees.

9. STATISTICAL ANALYSIS

9.1 General considerations

For the modified intention to treat analysis, all randomized patients who received at least one dose of study medication will be included. Missing data will be handled with multiple imputation, due to its nature of giving standard errors and P values that incorporate missing-data uncertainty²².

For the per protocol analyses, only randomized patients whose compliance was clear, and who received at least four days of trial medication (in clinical successes), or one day of trial medication (in clinical failures) will be included.

For the per protocol analysis of our primary outcome, patients are considered clinically cured if there is resolution of cellulitis at 14 days defined as disappearance of warmth and tenderness at the site of infection, with substantial improvement in erythema and edema, and without recurrence by day 28, defined as the need of additional antibiotic therapy for cellulitis. Clinical failure is defined as the persistence or progression of signs and symptoms of the acute process after randomization, or the inability to complete the study owing to adverse events. The response is deemed indeterminate when the patient (i) received less than 80% of the study drug for reasons other than clinical failure, (ii) acquired a concomitant infection outside of the skin requiring antibiotic treatment, (iii) was lost to follow-up, or (iv) died unrelated to the primary diagnosis.

For the per protocol analysis of our first secondary outcome (paragraph 7.1.2), patients are considered clinically cured if there is resolution of cellulitis at 14 days, defined as the absence of fever and an improvement of the combined symptom score of warmth, tenderness, erythema and edema by 2 or more points since patient inclusion (or it has reached 0), and without recurrence by day 28, defined as a stable or further improved combined symptom score, absence of fever and no need of additional antibiotic therapy for cellulitis. The response is deemed indeterminate when the patient (i) received less than 80% of the study drug for reasons other than unblinding / requiring new antibiotics for cellulitis / being unable to continue due to adverse effects, (ii) acquired a concomitant infection outside of the skin requiring antibiotic treatment, (iii) was lost to follow-up, or (iv) died unrelated to the primary diagnosis. Those whose outcomes are not cured or indeterminate are considered clinical failures.

We plan to conduct two subgroup analyses, based on biological plausible explanations, and statistically tested with interaction effects. Diabetes mellitus has recently been shown to affect outcome in patients treated for complicated skin and skin structure infections, through multiple suggested mechanisms²⁶. A high cellulitis severity score reflects an extensive local inflammatory response to infection, which might indicate a higher grade of infection that possibly requires more intensive or prolonged antibiotic therapy.

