9.4 Secondary study parameter(s)

Differences in secondary outcome parameters will be reported as relative risk or mean difference (with 95% confidence interval), and p-values for statistical significance estimated with the Chi-square test, t-test or Mann-Whitney test, where appropriate. A Kaplan-Meier analysis will be performed to compare the time to relapse (defined as requiring additional antibiotics for cellulitis) between the two groups.

Variable/outcome	Hypothesis	Outcome measure	Methods of analysis
1. Primary			
Resolution without relapse	Intervention not inferior to control	Percent cured on day 14 without relapse by day 28 [binary]	Absolute risk difference
2. Secondary			
Resolution without relapse (per definition of protocol version 9.4, see paragraph 7.1.2, including both sensitivity analysis and per protocol analysis)	Intervention not inferior to control	Percent cured on day 14 without relapse by day 28 [binary]	Absolute risk difference (Per protocol analysis: χ^2 → Relative Risk)
Relapse by day 90	No difference	Percent with relapse [binary]	χ^2 → Relative Risk
Time to relapse	No difference	Relapse after cure [time to event]	Kaplan-Meier survival analysis
Objective speed of recovery	No difference	Cellulitis severity score [continuous]	Student's T-test or Mann-Whitney U test
Subjective speed of recovery	No difference	Visual analogue scales of pain and swelling [continuous]	Student's T-test or Mann-Whitney U test
Quality of life	No difference	SF-36 questionnaire score at day 0 and 90 compared to population, day 14 and 28 compared to day 5-6 [continuous]	Student's T-test or Mann-Whitney U test
Antibiotic usage	No difference	Total costs of antibiotic use [continuous]	Student's T-test or Mann-Whitney U test
Health care utilization	No difference	Total treatment associated costs, Health Care Utilization Questionnaire [continuous]	Student's T-test or Mann-Whitney U test
3. Subgroup analyses			
Cellulitis severity score on a continuous scale	Severity score affects rate of cure		Regression analysis, with interaction term for severity score
Diabetes mellitus vs no diabetes mellitus	Diabetes affects rate of cure		Regression analysis, with interaction term for (no) diabetes
4. Sensitivity analyses	Intervention not inferior to	All outcomes	

	control		
Per protocol analysis			Chi ² → Relative Risk
Primary outcome adjusted for baseline covariates			Cochran-Mantel-Haenszel → Relative Risk

Table 3. Analysis methods per outcome measures or variables

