10.7 Risk assessment

The main risks of this study are a lower cure rate and a higher relapse rate of cellulitis in the 6-days treated arm. Keeping studies in other infectious diseases in mind, this risk seems small. Only clinically stable patients are included, critically ill patients as well as patients not responding to therapy the first 6 days are excluded. The small remaining risk is acceptable to us in view of the great advantages that a general shortening of antibiotic treatment of cellulitis would yield.

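### Does the per-protocol analysis of the primary outcome leave patients who resolve by day 14 and relapse by day 28 without a category?

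*Combined protocol and SAP*

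**What the plan says.** Section 9.1 gives the per-protocol rules in three steps.

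- **Entry to the set.** Compliance must be clear, and the set takes randomised patients "who received at least four days of trial medication (in clinical successes), or one day of trial medication (in clinical failures) will be included".
- **Primary outcome.** Cure needs resolution at 14 days and no further antibiotic treatment for cellulitis by day 28. On failure: "Clinical failure is defined as the persistence or progression of signs and symptoms of the acute process after randomization", or being unable to complete the study because of adverse events. Indeterminate has four listed reasons: the patient "received less than 80% of the study drug for reasons other than clinical failure", had an infection outside the skin that needed antibiotics, was lost to follow-up, or died of an unrelated cause.
- **First secondary outcome.** The 80% rule here applies "for reasons other than unblinding / requiring new antibiotics for cellulitis / being unable to continue due to adverse effects", and the paragraph closes with "Those whose outcomes are not cured or indeterminate are considered clinical failures".

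Table 3 in section 9.4 defines the primary outcome as the percentage cured on day 14 and free of relapse to day 28, marked as binary. It lists the per-protocol analysis under sensitivity analyses, with a chi-squared test and relative risk. The main analysis (sections 9.1 and 9.3) is the risk difference, with a one-sided 95% limit, in the modified intention-to-treat population.

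**The concern.** Take a patient who has resolved at day 14, took all the study drug, and needs antibiotics for cellulitis on day 20. This patient is not cured. The signs went away, so strictly they neither persisted nor progressed, and none of the four indeterminate reasons applies. For the first secondary outcome the closing sentence would make the patient a failure; the primary-outcome paragraph has no such sentence. Because the entry rule speaks only of successes and failures, one could argue that the patient drops out of the set.

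Relapse is central to this trial. Section 10.7 states: "The main risks of this study are a lower cure rate and a higher relapse rate of cellulitis in the 6-days treated arm". Section 8.2.2 exempts cellulitis readmissions from serious adverse event reporting "since a significant part of included patients is expected to be readmitted to the hospital due to relapse of cellulitis". A per-protocol check that dropped relapsers could look reassuring precisely when the short course was doing worse.

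A second apparent conflict concerns exposure. A success enters with four of six days, yet less than 80% of the study drug makes a response indeterminate.

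**Working it through.** **1. The plan's own figure.** Section 4.4 assumes 85% success in both arms, a 10-point margin, one-sided 0.05 and 80% power. n per arm = (1.645 + 0.842)² × 2 × 0.85 × 0.15 / 0.10² = 157.7, rounded up to 158, or 316 in total. This reproduces, and the point at issue does not affect it.

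**2. Where the relapser falls.** Study drug runs for six days after day 6 (section 5.1), so it ends at about day 12, before the day 14 assessment. A relapse after day 14 therefore cannot be the reason for short exposure. Two cases remain among patients with clear compliance and no other indeterminate reason:

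| Study drug taken | Consequence under 9.1 |
|---|---|
| At least 80% (4.8 of 6 days) | Meets both the four-day and the one-day minimum, so is in the set whatever the label; is not cured by definition |
| Under 80%, stopped for a reason other than failure | Indeterminate under reason (i) |

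In the first row, the binary outcome puts the patient in the denominator and not in the numerator. The word failure is not needed for that count.

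**3. The two exposure rules.** 4/6 = 66.7%, and 80% of 6 days is 4.8 days. A resolved patient with 4.0 to under 4.8 days is indeterminate, hence not a clinical success. Applied together, the rules give one answer: 80% governs, and the four-day minimum is redundant for successes.

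**4. What leaving relapsers out would do.** The rates are assumed; the documents give none by day 28. There are 158 patients per arm.

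- 12-day arm: 90% resolve and 5% of those relapse, so success = 0.90 × 0.95 = 0.855, relapse = 0.045, unresolved = 0.10.
- 6-day arm: success 0.765, a deficit of 0.09. A share f of the deficit is relapse, so relapse = 0.045 + 0.09f.
- Relapsers left out: success / (1 − relapse) in each arm. The 12-day arm becomes 0.855/0.955 = 0.895.

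| Handling | 6-day success | Difference (points) | Relative risk | Chi-squared p |
|---|---|---|---|---|
| Counted as not cured | 0.765 | -9.0 | 0.895 | 0.041 |
| Left out, f = 1 | 0.765/0.865 = 0.884 | -1.1 | 0.988 | 0.77 |
| Left out, f = 0.5 | 0.765/0.910 = 0.841 | -5.5 | 0.939 | 0.17 |
| Left out, f = 0 | 0.765/0.955 = 0.801 | -9.4 | 0.895 | 0.02 |

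**5. The main analysis at the same rates.** SE = √[(0.855 × 0.145 + 0.765 × 0.235)/158] = 0.0438. Lower limit = -9.0 − 1.645 × 4.38 = -16.2 points, beyond the 10-point margin. Two further assumed cases with more relapse in the 6-day arm behave alike:

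- Persistent failure 10% in both arms, relapse 5% against 10%: difference -5.0, lower limit -12.0 with relapsers counted; -6.6 with them left out.
- Persistent failure 5% in both arms, relapse 10% against 20%: difference -10.0, lower limit -17.3 with relapsers counted; -5.4 with them left out.

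With equal relapse in both arms the difference is 0 under either handling.

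**The case for a change.** The best argument for a change is that section 9.1 departs from a plain binary outcome in this analysis by adding an indeterminate class, so not cured no longer means failed. Adjacent paragraphs that differ invite the reading that the difference is deliberate. Table 3 places the per-protocol analysis under a non-inferiority hypothesis, and dropping relapsers would blunt it. One added sentence would cost nothing.

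The textual part stands: relapse is unnamed and the catch-all is missing. The same omission leaves a death from cellulitis without an explicit label. The inference does not follow. The indeterminate list is closed and relapse is not on it, so the third class gives no ground for removing these patients. The cure sentence was written to exclude recurrence by day 28, which would be pointless if recurrent patients were then dropped. Nothing suggests that the two paragraphs were meant to treat relapse differently.

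The scale of relapse is also uncertain. The 12 to 20% in section 1 would be 38 to 63 of 316 patients, but it has no time window and the title of one of its two cited sources refers to a 1-year follow-up. It cannot be set against a day 28 endpoint. The readmission remark in section 8.2.2 concerns all included patients, some of whom are never randomised.

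**Conclusion.** No change to the plan follows. This is a gap that analysts fill sensibly: cure excludes recurrence, the outcome is binary, and a compliant relapser is in the set under either exposure minimum, so the patient counts as not cured. Copying the catch-all across would only write down that result.

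The distortion from leaving relapsers out would not be small if it happened: up to 7.9 points in the main illustration (-9.0 against -1.1). It rests on assumed rates and on the least natural reading of section 9.1, and it disappears when none of the deficit is relapse. It is confined to a sensitivity analysis. The modified intention-to-treat test counts every relapse by day 28 as a non-success, and in each of the illustrations with a deficit it already misses the margin. Relapse by day 90 and time to relapse are compared between arms separately, and the per-protocol analysis of the first secondary outcome handles relapse explicitly.

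The conclusion depends on the analyst reading section 9.1 together with Table 3. A per-protocol result that omitted relapsers would depart from the plan's own definition of the outcome.

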3.3 Time schedule of study procedures for participants

	Day 0	Day 2-3	Day 5-6	Day 14-15	Day 28-29	Day 90
Informed consent	X					
In- and exclusion criteria	X					
Physical examination	X		X	X	X	
Laboratory measurements (usual care)	X					
Venous puncture	X	X	X	X	X	
Skin biopsy (see chapter 7)	X					
Clinical cellulitis score	X	X	X	X	X	
Self assessment score (0-10 scale)	X	X	X	X	X	X
SF-36 questionnaire & EQ-5D	X				X	X
Health care utilization questionnaire			X		X	X
Skin swabs (see chapter 7)	X			X		

Table 1. Time table of study procedures for participants

Up to day 28-29, patients will be evaluated face to face either in the clinic or at home. Self assessment scores and questionnaires to be performed on day 90 will be mailed to patients beforehand. On day 90, the investigators will review the answers and scores by telephone. Laboratory measurements collected through usual care will be collected when available. In exceptional cases, where inclusion would be hampered by people's willingness or ability to have so many follow-up visits, the decision can be made by the investigators to perform the day 28-29 visit solely by telephone. In this case the primary endpoint, questionnaires and medication information would be assessable. Physical examination, cellulitis severity score measurement and blood collection will not be possible.

The above table displays the ideal time schedule for participants. However, patients can be included until 72 hours after admission. When patients are included during 24-72 hours, the day 2-3 visit is skipped. The check for improvement on day 5-6 then also allows for self-reported improvement as marker for clinical improvement, due to the investigator not being present at the time when the disease was likely at its most severe. Self-reported improvement is also rated using the seven aspects of the cellulitis severity score; patients will be asked if they think that they have improved, taking all those aspects into account.

[figure not shown]

Figure 1. Flow diagram for study participants**3.4 Time schedule of the study**

Months 1-4:	Preparation of study and obtaining ethical approval
Months 5-44:	Enrolment of patients
Month 44:	Last patient enrolled
Month 47:	Last follow-up visit of last enrolled patient
Months 47-48:	Analysis of results

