4.3 Exclusion criteria

As this study focuses on the treatment of cellulitis requiring hospitalization without additional complicating factors, a potential subject who meets any of the following criteria will be excluded from participation:

- Allergy for flucloxacillin, other beta-lactam antibiotics or one of the additives, or flucloxacillin induced hepatitis or liver enzyme disorders.
- Concurrent use of antibiotics for other indications
- Alternative diagnosis accounting for the clinical presentation.
- All cases involving any of the following complicating factors:
 - o Use of antibiotics with Gram-positive activity for more than 4 days in the past 7 days
 - o Intensive care unit admission during the last 7 days
 - o Risk factors associated with Gram-negative pathogens as a causative agent¹⁹:
 - o Chronic or macerated infra-malleolar ulcers, or infra-malleolar ulcers with previous antibiotic treatment, in patients with diabetes mellitus²⁰
 - o Neutropenia
 - o Cirrhosis (Child-Pugh class B or C)
 - o Intravenous drug use
 - o Human or animal bite
 - o Skin laceration acquired in fresh or salt open water
 - o Fish fin or bone injuries
 - o Severe peripheral arterial disease (Fontaine IV)
 - o Severe cellulitis necessitating surgical debridement or fascial biopsy
 - o Necrotizing fasciitis
 - o Periorbital or perirectal involvement
 - o Surgery
 - o Life expectancy less than one month

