4.4 Sample size calculation

The sample size calculation of is based on three large randomised clinical trials which were published in high impact journals in 2014. From the DISCOVER, ESTABLISH and SOLO trials, information was gathered on cellulitis clinical cure rates as assessed by investigators after therapy:

DISCOVER²¹ (dalbavancin vs vancomycin-linezolid): (information from supplementary data)

- Clinical status evaluation at the end of therapy (day 14) of cellulitis patients:
 - o Cured: 297/324 and 276/301

ESTABLISH²⁷ (tedizolid vs linezolid): (information received from authors via e-mail)

- Investigator assessed response at post-therapy evaluation (7-14 days after end of therapy) of cellulitis patients:
 - o Cured: 265/301 and 263/307

SOLO²⁸ (oritavancin vs vancomycin): (information received from authors via e-mail)

- Investigator assessed clinical cure rates at the post-therapy evaluation (7-10 days after end of therapy) of cellulitis patients:
 - o Cured: 294/387 and 315/400

Total cure rates:

- $$(297+276+265+263+294+315) / (324+301+301+307+387+400) = 1710 / 2020 = 84,65\% \text{ cure rate}$$

A two-group large-sample normal approximation test of proportions with a one-sided 0.050 significance level will have 80% power to reject the null-hypothesis, assuming a success rate

of 85% and considering a difference of 10% between the two groups as equivalence limit, if the sample size of each group is 158. This gives a total sample size of 316 patients.

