5. TREATMENT OF SUBJECTS

5.1 Investigational product/treatment

After 5-6 days of treatment, patients who respond to therapy – defined as absence of fever (defined as temp $> 38.0^{\circ}\text{C}$) and clinical improvement since admission (either self-reported or investigator-assessed using the cellulitis severity score) – will be randomized in a blinded fashion with a 1:1 allocation ratio to receive 6 more days of (A) oral flucloxacillin or (B) oral placebo (both starting after day 6):

- (A) Regular treatment group: after the initial 6 days of flucloxacillin, another 6 days of oral flucloxacillin.
- (B) Intervention group: after the initial 6 days of flucloxacillin, 6 days of oral placebo.

Flucloxacillin treatment is administered as currently advised by the SWAB⁹: flucloxacillin intravenously 1000mg 4dd or orally 500mg 4dd, as a minimum. Some physicians will decide to dose differently, such as intravenously 1000mg 6dd, or orally 1000mg 4-6dd. This is allowed, but will be documented and can be taken into account during the analyses. No added benefit is to be expected from higher or more frequent dosing. Empirical treatment on admission can differ from flucloxacillin, provided it contains a beta-lactam antibiotic with anti-staphylococcal activity. Switch from intravenous medication to the oral route can be initiated before the 6th day of treatment at the discretion of the attending physician, but only if the patient has no fever (temp $> 38.0^{\circ}\text{C}$) and when the physician is convinced the cellulitis is improving. Patients who do not respond to treatment or whose blood cultures became positive (excluding contamination related positive blood cultures) will not be randomized and will be treated at the discretion of the attending physician. Their definitive diagnosis upon discharge, definitive antibiotic treatment and discharge date will be recorded.

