7. METHODS

7.1 Study endpoints

7.1.1 Main study endpoint

The primary endpoint is resolution of cellulitis at 14-15 days, defined as disappearance of warmth and tenderness at the site of infection, with substantial improvement in erythema and edema, and without recurrence by day 28-29, defined as the need of additional antibiotic therapy for cellulitis.

This endpoint is in accordance with the study by Hepburn et al¹², and assumes that erythema and edema take longer to resolve than warmth and tenderness as seen in clinical practice.

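### The per-protocol rules can keep a placebo patient given other Gram-positive antibiotics as a short-course cure and can drop a documented failure, and the bar on other antibiotics is not restated at randomisation

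*Combined protocol and SAP*

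**What the plan says.** **Before randomisation.** Section 4.3 lists "Concurrent use of antibiotics for other indications" as an exclusion. In Table 1 (section 3.3) the row "In- and exclusion criteria" is marked in the day 0 column only; the text below the table allows inclusion up to 72 hours after admission. At day 5-6, sections 5.1 and 7.2 require a response to initial therapy (no fever, clinical improvement), and 5.1 withholds randomisation from "Patients who do not respond to treatment or whose blood cultures became positive", contaminated cultures aside. Neither section mentions other antibiotics. Section 5.2 leaves other treatment to daily practice.

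**Endpoint.** In 7.1.1 recurrence is "defined as the need of additional antibiotic therapy for cellulitis". An antibiotic given for anything else does not count against cure. The modified intention-to-treat set in 9.1 has no rule for such use.

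**Per-protocol definitions (9.1).** For the primary and the first secondary outcome alike, rule (ii) makes the response indeterminate if the patient "acquired a concomitant infection outside of the skin requiring antibiotic treatment". Rule (i) does so if under 80% of study drug was taken, with stated exceptions; rules (iii) and (iv) cover loss to follow-up and unrelated death. Entry needs clear compliance and at least four days of trial medication for successes, or one day for failures. For the first secondary outcome, failures are whoever is left after cured and indeterminate patients are set aside. For the primary outcome, failure and indeterminate each have their own definition, and no order between them is given.

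**The concern.** The trial compares 6 with 12 days of active treatment. Other Gram-positive cover in the placebo arm shrinks that contrast. The 12-day arm already has active drug, so a rule that is the same for both arms does not act equally on them. The arms move together, which is the unsafe direction in a non-inferiority trial.

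Analysing patients as randomised is legitimate and accepts this dilution. The per-protocol analysis is therefore where one would look for a check on it, and rule (ii) stops at infections outside the skin. The study population carries ulcers, eczema, trauma and burns as listed risk factors (Table 2), so other skin infections are plausible. An antibiotic begun between inclusion and day 5-6 could also contribute to the response that qualifies the patient for randomisation.

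The order of categories is a separate matter. If indeterminate overrides failure, failures that have already been documented leave the per-protocol comparison.

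**Working it through.** **1. The plan's sample size.** Inputs from 4.4: a "one-sided 0.050 significance level will have 80% power to reject the null-hypothesis" and, for the assumed cure proportion and margin, "of 85% and considering a difference of 10% between the two groups as equivalence limit, if the sample size of each group is 158". With the unpooled normal approximation:

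n per arm = (1.645 + 0.842)² × 2 × 0.85 × 0.15 / 0.10² = 6.18 × 25.5 = 157.7, rounded up to 158, or 316 in total.

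This agrees with the plan: "This gives a total sample size of 316 patients". Power at 158 per arm is 80.1%.

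**2. Four patients followed through the rules.**

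| Patient | Modified intention-to-treat | Per protocol |
|---|---|---|
| Placebo; antibiotic for a non-skin infection; signs resolve | Cure | Indeterminate, rule (ii) |
| Placebo; other antibiotic replaces study drug, under 80% taken; signs resolve | Cure | Indeterminate, rule (i) |
| Placebo; keeps taking study drug; Gram-positive-active antibiotic for a non-cellulitis skin infection or a non-infection reason; signs resolve | Cure | **Cure: no rule applies** |
| Extra antibiotics for cellulitis on day 9, pneumonia treated on day 20 (first secondary outcome) | Failure | **Indeterminate: removed** |

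The fourth row follows because failure is the residual category there. Rule (i) exempts patients who needed new antibiotics for cellulitis, but rules (ii) and (iii) have no such exemption. Loss to follow-up after the rescue gives the same result. For the primary per-protocol outcome such a patient could meet both definitions, and the text does not say which prevails.

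**3. Possible size of dilution (illustration).** The documents give no rate of other antibiotic use, so the covered share f of the placebo arm is an assumption. A second assumption is that cover removes all excess failure. With true success 85% v 75%:

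- placebo-arm success p = 0.75 + 0.10f; difference d = 0.85 − p
- SE = √[(0.85 × 0.15 + p(1 − p)) / 158]
- P(declare non-inferiority) = Φ[(0.10 − d)/SE − 1.645]

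For f = 0.05: p = 0.755, d = 0.095, SE = √(0.312475/158) = 0.0445, and Φ(0.005/0.0445 − 1.645) = Φ(−1.53) = 6.3%.

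| f | Placebo patients | Difference | False non-inferiority | Exact binomial |
|---|---|---|---|---|
| 0 | 0 | 10.0 points | 5.0% | 5.2% |
| 2% | about 3 | 9.8 | 5.5% | 5.7% |
| 5% | about 8 | 9.5 | 6.3% | 6.5% |
| 10% | about 16 | 9.0 | 7.8% | 8.0% |

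These rates describe the modified intention-to-treat test at 158 per arm. They do not give the error of the per-protocol analysis.

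**The case against.** The strongest reply is that little of this touches the primary analysis. Counting patients by their cellulitis outcome as randomised is ordinary practice, and rewording the per-protocol definitions leaves that test and its error rate unchanged. This stands.

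Several stronger readings are tempting, and the text does not support them:

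- *Rule (ii) is the only thing that removes such patients per protocol.* It is not. Rule (i), the compliance condition and the four-day minimum already remove many whose study drug was stopped or replaced.
- *Any treated ulcer or eczema infection escapes.* The definition of cellulitis in 4.2 and Appendix I is broad. An infected ulcer or eczema with warmth, erythema and induration can fall under it, and treatment then counts as recurrence.
- *Receiving the antibiotic makes the patient a cure.* The day-14 signs must still resolve.
- *Nothing is checked at randomisation.* Section 7.2 mentions built-in eCRF checks whose content is not shown. What can be said is that the protocol states no re-check. Rule (ii) also has no start date, so a non-skin infection treated on day 4 may still make the patient indeterminate per protocol.

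A further objection concerns the remedy. Making every patient with other Gram-positive cover indeterminate would also drop those whose signs persist at day 14, who now count as failures and may show harm from short treatment. That is right, and the fix below is limited accordingly.

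Finally, the illustration assumes complete protection, although cover begun on day 20 cannot stand in for days 7 to 12. It therefore leans high for any given share.

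**Conclusion.** The point holds in a limited form. Three gaps are in the text: the exclusion for concurrent antibiotics is not restated as a condition for randomisation; rule (ii) misses Gram-positive cover for non-cellulitis skin infections or non-infection reasons in patients who keep taking study drug and whose signs resolve; and documented failure has no precedence over indeterminate. The first two can only be expected to narrow the contrast between arms, and the third can remove failures from the per-protocol comparison.

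The size is unknown. Under the two assumptions above, false non-inferiority in the modified intention-to-treat test would be 5.5% to 7.8% for a covered share of 2% to 10%, against 5.0%. A reader might infer that the trial's error rate is inflated by that much, but no documented rate of use supports this. The category-order gap does not depend on that share. It needs an uncommon sequence of events, and in the modified intention-to-treat analysis a patient given extra antibiotics for cellulitis remains a failure. The changes are worth making because they are cheap and remove a bias towards non-inferiority from the supporting analysis.

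**What to change.** 1. **Section 9.1, both per-protocol definitions:** state that a documented failure (signs not meeting the day-14 criteria, or additional antibiotics for cellulitis by day 28) takes precedence over indeterminate.
2. **Section 9.1, rule (ii):** extend it to any systemic antibiotic with Gram-positive activity given between randomisation and day 28 for a reason other than the study cellulitis, whatever the site. Apply it only to patients who would otherwise be cured, so that failures stay in. Report such use by arm.
3. **Table 1, 5.1 and 7.2:** repeat the protocol's own 4.3 exclusion for concurrent antibiotics at the day 5-6 check before randomisation, including for patients preliminarily randomised ahead of a weekend.

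Cost: protocol and SAP wording and one item at day 5-6. Antibiotic use is already collected (7.3.4, 11.1), and the sample size does not change. The per-protocol set becomes slightly smaller and a few enrolled patients are not randomised. Item 2 makes exclusion depend on outcome, as the differing minimum exposure for successes and failures in 9.1 already does, so the result should be read beside the modified intention-to-treat analysis. Items 1 and 2 do not alter that analysis; item 3 affects only cover begun before randomisation.
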